We further let the parameters $\theta_j = \log(\pi_j / (1 - \pi_j))$ (logistic transformation) be either exchangeable with some of the tumor types, or non-exchangeable with any of them. Based on the number of strata in this trial, we allow for two exchangeability distributions, which, for example, accounts for the case where some tumor type show no efficacy and some are promising. Thus, for each tumor type j , three possibilities arise, with respective probabilities $p_j = (p_{j1}, p_{j2}, p_{j3})$, as follows:

1. With probability p_{j1} (probability group j belongs to exchangeability set 1) the parameter θ_j follows a normal distribution with exchangeability parameters μ_1 and τ_1 :

$$\theta_j \sim N(\mu_1, \tau_1^2)$$

2. With probability p_{j2} (probability group j belongs to exchangeability set 2) θ_j follows a normal distribution with exchangeability parameters $\mu_1 < \mu_2$ and τ_2 :

$$\theta_j \sim N(\mu_2, \tau_2^2)$$

3. With remaining probability $p_{j3} = 1 - p_{j1} - p_{j2}$ (probability group j is not exchangeable with any other group), θ_j follows a weakly-informative prior distribution

$$\theta_j \sim N(m_w, v_w)$$

For the detailed specifications of m_w , v_w , the a-priori weights p_j ($j=1, \dots, J$), and the prior distributions for μ_1 , τ_1 , μ_2 , and τ_2 , see (Appendix 4). At any given time of the trial, including at the end, posterior probabilities of the various parameters will be estimated using Markov chain Monte Carlo methods.

The results at the final analysis within a tumor type will be regarded to be positive if both of the following conditions are met:

- a. posterior mean \geq “clinically meaningful activity” threshold (column for C2 in Table 10-1) (i.e. posterior mean ORR \geq C2)
- b. Posterior probability of “not being clinically meaningful” (column for C1 in Table 10-1) is less than 10% (i.e., $\text{prob}(\text{ORR} \leq \text{C1} | \text{data}) < 10\%$)

[figure not shown]

Table 10-1 Type of tumors of interest with definition of being clinically meaningful

Disease Code	Tumor type	Not Clinically meaningful (C ₁)	Clinically meaningful (C ₂)
T1	DLBCL ^a	<= 10%	>= 20%
T2	Pancreatic ^b	<= 8%	>= 16%
T3	HNSCC naive ^c	<= 13%	>= 23%
T4	Urothelial ^d	<= 15%	>= 27%
T5	RCC naive at 160 mg	<= 25%	>= 37%
T6	TNBC ^g	<= 5%	>= 13%
T7	Melanoma pretreated ^h	<= 10%	>= 25%
T8	HNSCC pretreated	<= 5%	>= 13%
T9	MSS CRC – RAS wildtype ^f	<= 5%	>= 13%
T10	MSS CRC – RAS mutant ^f	<= 5%	>= 13%

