10.7 Interim analysis

Part 1:

Patients will be continuously accrued and the data will be analyzed using a Bayesian hierarchical model mentioned in [Section 10.4.2](#). Interim analysis for a tumor type will be performed when at least 10 patients which have been enrolled for that tumor type at the same dose level have at least one post-baseline disease assessment, except for MSS-CRC RAS wildtype, MSS-CRC RAS mutant and RCC IO naive at 240 mg patients, in which no interim analysis will be done. The futility analysis will not be binding. At each of these analyses, the current (posterior) probability that the response rate for each of the tumor types is greater than “clinically meaningful threshold (column for C2 in [Table 10-1](#))” will be determined.

These probabilities will be used to adapt the design. All available data for evaluable patients (defined in [Section 10.4.3](#)) will be used for analysis at each interim analysis. However, a decision will be made for all tumor types with minimum of 10 patients (who have at least one post-baseline assessment). For a specific tumor type, a decision will be made based on the calculated probability as given below:

1. Accrual to a tumor type (with minimum sample size requirement described above) will cease for futility if it is very unlikely (posterior probability <20%) that the response rate for the tumor type is “clinically meaningful” (\geq C2 threshold in [Table 10-1](#))
2. Otherwise, recruitment will continue until the next IA is performed or a maximum of 30 patients in that tumor type has been enrolled.

For the purpose of the IA, if a patient is still on study and the last available efficacy assessment is a PR/CR which is yet to be confirmed by a subsequent scan, then this patient will be considered as a responder.

The results at the final analysis within a tumor type will be regarded as positive if the posterior mean ORR is greater than the threshold for clinically relevant activity and the posterior probability of not being clinically meaningful is low (less than 10%).

Depending on enrollment, there may be multiple interim analyses.

Japanese safety run-in part

No formal interim analyses are planned. However, the dose-escalation design for safety run-in part foresees that decisions based on the current data are taken before the end of the planned safety run-in part. Details of this procedure and the process for communication with Investigators are provided in [Section 4.1.4](#).

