10.8 Sample size calculation

Part 1:

The design of this part is adaptive in nature; hence, the final sample size is not fixed. A minimum of 10 evaluable patients and a maximum of 30 treated patients in each tumor type T1 through T13 will receive treatment. Thus, the total sample size across all tumor types will be between 130 and 310.

Patients will be continuously accrued, and, the accumulated data will be analyzed at interim as described in [Section 10.7](#). Based upon the results of any of these analyses, enrollment into one or more tumor types may be terminated.

The operating characteristics for this Bayesian Design are evaluated using simulation. Simulation-based probability estimates (relative frequencies) of futility at interim and positive results at final analysis for each tumor type in four scenarios (see [Table 14-12](#)) are provided in [Appendix 4](#). The number of simulations generated for each scenario is 1000. For additional details, please see [Appendix 4](#). Presented below is a summary of the operating characteristics based on eight tumor types included in the initial protocol design prior to interim analysis:

[Table 14-13](#) (Scenario 1) presents the operating characteristics of the design when the true underlying ORR of none the eight tumor types is clinically meaningful (in other words, null case for all tumor types). The false positive rate (for final analysis) for each of the tumor types are appropriately controlled, ranging between 2.6% and 6.8%. Similarly, the chances of stopping for futility at IA are high, ranging from 45.8% to 69.7%.

[Table 14-14](#) presents the operating characteristics for two scenarios (2a and 2b):

- Scenario 2a presents the operating characteristics when the true underlying ORR of all the eight tumor types is clinically meaningful (in other words, alternative case for all tumor types). The probability of positive conclusion (for final analysis) for each of the tumor types are appropriately high, ranging between 78.2% and 90.7%. Similarly, the chances of stopping for futility at IA are low, ranging between 3% and 11.9%.
- Scenario 2b, in contrast to Scenario 2a, presents the case where, out of all eight tumor types there is one single tumor type (T4-Bladder) which does not have clinically meaningful ORR while all other seven tumor types have clinically meaningful ORR. However, the model adapts appropriately and the false positive rate (1.1%) for T4 is

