effectively controlled. For the rest seven tumor types which have clinically meaningful ORR (same as Scenario 2a), the probability of positive conclusion has slightly changed (vs Scenario 2a) but remained acceptably high (ranging between 79.6% and 88.7%).

Table 14-15 (Scenario 3) presents the operating characteristics when four tumor types have clinically meaningful ORR while the other four do not have clinically meaningful ORR. In this scenario as well, the false positive rates for the inactive tumor types are properly controlled (4.9% - 6.9%) while the probability of positive conclusion for the active tumor types are high (78.2% - 86.6%).

Similar operating characteristics are expected based on the thirteen tumor groups.

Part 2:

At least 20 patients will be enrolled in each of the dosing schedules. Table 10-3 shows the posterior mean and corresponding 90% credible interval for N = 20 (since it is planned to have approximately 20 patients in each schedule) for various observed ORR using a minimally informative unimodal beta prior distribution with parameters $a = 1/3$ and $b = 1$ (note: this assumes a priori response rate of 25%). This is same for all dosing schedules.

Table 10-3 Posterior summaries for given number of responses (ORR)

Observed ORR (N, %)	Posterior mean (90% credible interval)	Probability of no improvement [0% - 20%]	Probability of limited improvement [20% - 33%]	Probability of clinically meaningful improvement [33%-100%]
0 (0%)	0.016 (0.00,0.070)	0.999	0.001	0.000
3 (15%)	0.156 (0.051, 0.299)	0.744	0.228	0.028
4 (20%)	0.203 (0.081, 0.356)	0.534	0.385	0.080
5 (25%)	0.250 (0.115, 0.414)	0.316	0.498	0.185
10 (50%)	0.484 (0.311, 0.657)	0.002	0.070	0.928
15 (75%)	0.718 (0.548, 0.863)	0	0	1
20 (100%)	0.954 (0.866,0.997)	0	0	1

From Table 10-3, with a sample size of 20 patients, if the observed ORR is 25%, the probability of true ORR to be at least 33% is 18.5%. If the observed ORR is 50%, the probability of true ORR to be at least 33% is 92.8%. Also, with a sample size of 20, if the observed ORR is 15%, the probability of true ORR to be less than 20% is 74.4%.

Table 10-4 shows the posterior probability that ORR for schedule 1 (S1) is greater than ORR for schedule 2 (S2) for various observed ORR using a minimally informative unimodal beta prior distribution with parameters $a = 1/3$ and $b = 1$. Similar approach can be used to compare schedule 2 to schedule 3 and schedule 1 to schedule 3.

[figure not shown]

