14.4.3.2.1 Metrics to assess operating characteristics

In a given tumor type, the type I error (false positive rate) of the adaptive design can be viewed as the probability estimate of a positive conclusion at final analysis in Scenario 1 ([Table 14-13](#)). The power of the adaptive design is defined as the probability estimate of positive conclusion at final analysis in Scenario 2a ([Table 14-14](#)).

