14.4.3.2.2 Results

Table 14-13 (Scenario 1) presents the operating characteristics of the design when the true underlying ORR of none the eight tumor types is clinically meaningful (in other words, null case for all tumor types). The false positive rate (for final analysis) for each of the tumor types are appropriately controlled, ranging between 2.6% and 6.8%. Similarly, the chances of stopping for futility at IA are high, ranging from 45.8% to 69.7%.

Table 14-13 Simulation results for Scenario 1 (NIR178 and PDR001 combination inactive for all tumor types)

Disease code	Tumor type	True ORR (%)	Probability of stopping at IA for futility (%)	Probability for positive conclusion in final analysis (%)
T1	DLBCL	10.0	64.3	4.2
T2	Pancreatic	8.0	45.8	6.8
T3	H&N	13.0	61.9	5.1
T4	Bladder	15.0	65.7	2.6
T5	RCC	25.0	69.7	4.1
T6	Colon (MSS)	5.0	59.8	5.8
T7	TNBC	5.0	59.8	5.8
T8	Melanoma	30.0	65.0	3.8

Table 14-14 presents the operating characteristics for two scenarios (2a and 2b):

- Scenario 2a presents the operating characteristics when the true underlying ORR of all the eight tumor types is clinically meaningful (in other words, alternative case for all tumor types). The probability of positive conclusion (for final analysis) for each of the tumor types are appropriately high, ranging between 78.2% and 90.7%. Similarly, the chances of stopping for futility at IA are low, ranging between 3% and 11.9%.
- Scenario 2b, in contrast to Scenario 2a, presents the case where, out of all eight tumor types there is one single tumor type (T4-Bladder) which does not have clinically meaningful ORR while all other seven tumor types have clinically meaningful ORR. However, the model adapts appropriately and the false positive rate (1.1%) for T4 is effectively controlled. For the rest seven tumor types which have clinically meaningful ORR (same as Scenario 2a), the probability of positive conclusion has slightly changed (vs Scenario 2a) but remained acceptably high (ranging between 79.6% and 88.7%).

[figure not shown]

Table 14-14 Simulation results for Scenario 2a (all tumor types active) and Scenario 2b (one single tumor type [T4-Bladder] inactive, all other active)

Disease code	Tumor type	True ORR (%)		Probability of stopping at IA for futility (%)		Probability for positive conclusion in final analysis (%)	
		2a	2b	2a	2b	2a	2b
T1	DLBCL	30.0	30.0	3.0	4.0	90.7	88.7
T2	Pancreatic	25.0	25.0	6.6	6.6	86.7	86.2
T3	H&N	35.0	35.0	4.5	6.7	90.5	87.6

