14.4.4 Hypothetical scenario testing after addition of new groups

This section was added after the inclusion of MSS CRC RAS mutant, MSS CRC RAS wildtype and HNSCC pretreated groups. For the updated version with 13 tumor groups, please see [Section 14.4.5](#).

This section shows on-study decisions made under the model after the new groups are added. The hypothetical data scenarios for interim and final analysis can be found in [Table 14-16](#) and [Table 14-17](#) respectively. For each scenario, the posterior probability of being “clinically meaningful” and “not clinically meaningful” (T1-T10 in [Table 10-1](#)) are calculated by group and displayed in the tables.

[Table 14-16](#) shows 6 different scenarios for interim analyses. The scenarios show one or more groups having 10 or more patients. It is to be noted that the decision to stop or continue enrollment of patients in that group is made only if the number of patients in that group is at least 10. Otherwise, no decision is made. As stated in [Section 10.7](#) at interim, a group is stopped if the probability of being “clinically meaningful” is less than 20%.

[figure not shown]
Scenario 1 and 2 shows two possible scenarios with the current data. There are 17 MSS CRC patients with 1 responder. The data for mutation status of CRC patients are not available but will be collected retrospectively after implementation of this protocol amendment. Hence, two different scenarios are considered. In scenario 1, we considered 2 out of the 17 patients are RAS mutant patients and 15 out of 17 patients have RAS status unknown. Hence the patients with unknown RAS status are not included in the model. One of the two RAS mutant patients is a responder. In scenario 2, we considered 2 out of 17 patients are RAS mutant patients and 7 out of 17 patients are RAS wildtype patients. The other 8 patients have RAS status unknown. One of the two RAS mutant patients is a responder. We will have 20 additional patients in the MSS CRC RAS wildtype and mutant group after expansion.

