- Scenario 2b, in contrast to Scenario 2a, presents the case where, out of all eight tumor types there is one single tumor type (T4-Bladder) which does not have clinically meaningful ORR while all other seven tumor types have clinically meaningful ORR. However, the model adapts appropriately and the false positive rate (1.1%) for T4 is effectively controlled. For the rest seven tumor types which have clinically meaningful ORR (same as Scenario 2a), the probability of positive conclusion has slightly changed (vs Scenario 2a) but remained acceptably high (ranging between 79.6% and 88.7%).

Protocol Table 14-15 (Scenario 3) presents the operating characteristics when four tumor types have clinically meaningful ORR while the other four do not have clinically meaningful ORR. In this scenario as well, the false positive rates for the inactive tumor types are properly controlled (4.9% - 6.9%) while the probability of positive conclusion for the active tumor types are high (78.2% - 86.6%).

Note:

Simulations were run after the inclusion of MSS CRC RAS mutant, MSS CRC RAS wildtype and HNSCC pretreated groups that show on-study decisions made under the model after the new groups are added (refer Protocol Section 14.4.4). The hypothetical data scenarios for interim and final analysis can be found in Protocol Table 14-16 and Protocol Table 14-17 respectively. For each scenario, the posterior probability of being “clinically meaningful” and “not clinically meaningful” (T1-T10 in Protocol Table 10-1) are calculated by group and displayed in the tables.

Similar exercise was conducted with the three additional tumor groups included in the protocol amendment 5 (i.e RCC IO naive, RCC IO pretreated patients and mCRPC, all treated at 240 mg BID dose of NIR178 in combination with PDR001) (refer Protocol Section 14.4.5). The hypothetical data scenarios for interim and final analysis can be found in Protocol Table 14-18 and Protocol Table 14-19 respectively.

3.2 Part 2

At least 20 patients will be enrolled in each of the dosing schedules.

[Table 3-1](#) shows the posterior mean and corresponding 90% credible interval for $N = 20$ (since it is planned to have approximately 20 patients in each schedule) for various observed ORR using a minimally informative unimodal beta prior distribution with parameters $a = 1/3$ and $b = 1$ (Note: this assumes a priori response rate of 25%). This is same for all dosing schedules.

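### No operating characteristics are reported for the 13-group Part 1 design, and the expectation that they match the 8-group figures is not supported for the two MSS CRC groups

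*Protocol*

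**What the plan says.** Protocol Section 10.8 introduces its Part 1 figures with "Presented below is a summary of the operating characteristics based on eight tumor types included in the initial protocol design prior to interim analysis". The figures come from Tables 14-13 to 14-15 (Appendix 4, Section 14.4.3), at 1,000 simulations per scenario. For the all-inactive scenario the text reads "The false positive rate (for final analysis) for each of the tumor types are appropriately controlled, ranging between 2.6% and 6.8"%. For the mixed scenario the inactive groups lie between 4.9% and 6.9%. Section 14.4.3.2.1 defines the error rate through the all-inactive scenario: "the type I error (false positive rate) of the adaptive design can be viewed as the probability estimate of a positive conclusion".

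For the current design Section 10.8 offers one sentence: "Similar operating characteristics are expected based on the thirteen tumor groups".

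SAP Section 3.1 repeats the 8-group results and adds in a note: "Simulations were run after the inclusion of MSS CRC RAS mutant, MSS CRC RAS wildtype and HNSCC pretreated groups". It cites Protocol Tables 14-16 and 14-17 and describes a similar exercise for Tables 14-18 and 14-19. Protocol Section 14.4.4 describes its own content differently: "This section shows on-study decisions made under the model after the new groups are added".

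**The concern.** The design that was simulated and the design that is analysed differ in features that drive error rates:

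- **MSS CRC.** It was one group with an interim at 10 patients, stopped 59.8% of the time under the null (Table 14-13). It is now two groups with no interim (Sections 4.2.1 and 10.7, Table 10-1 footnote) and 20 additional patients each.
- **T12** (RCC naive, 240 mg) also has no interim.
- **Melanoma** had a null rate of 30% and C2 of 43%. It now has C1 of 10% and C2 of 25%.
- **Number of groups.** Five more groups take part in the borrowing.

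A positive call needs a posterior mean of at least C2 and less than 10% posterior probability that ORR is at or below C1. The posterior mean depends on what the other groups do. Without a futility look, nothing removes an inactive MSS CRC group before that test. What is at stake is how far a positive MSS CRC result could be trusted, and whether the per-group error control described in Section 10.8 has been shown for the design in use.

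**Working it through.** **1. What the added-group tables contain.** Tables 14-16 to 14-19 are titled as hypothetical data scenarios. Each scenario is one data set with a posterior summary and a decision per group. None gives a false-positive rate, power or stopping probability.

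**2. Inputs.**
- Priors from Table 14-9: mu1 ~ N(-1.735, 2.789²), mu2 ~ N(0.405, 2.026²), both tau half-normal with scale 0.25, non-exchangeable N(-2.197, 3²), weights 0.25/0.25/0.50.
- Thresholds from Table 10-1. For T9 and T10, C1 = 5% and C2 = 13%.
- Interim at 10 patients, stopping if P(ORR ≥ C2) < 20%, except in T9, T10 and T12.
- Final n = 30, except T12 = 20 (assumed) and T9/T10 varied from 20 to 30.

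The posterior was computed by grid integration and the trial was then simulated.

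**3. Reproducing the plan's figures (8 groups, 2,000 trials).** Scenario 1 false positives, T1 to T8:
- stated 4.2, 6.8, 5.1, 2.6, 4.1, 5.8, 5.8, 3.8%
- recomputed 2.2, 6.0, 4.2, 2.9, 3.0, 4.9, 5.0, 3.4%

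Scenario 1 interim stopping was 44.7-71.2% (stated 45.8-69.7%). Scenario 2a power was 79.2-91.4% (stated 78.2-90.7%). Scenario 3 false positives were 3.8-5.8% (stated 4.9-6.9%). Agreement is close, and the recomputed error rates are mostly a little lower than the published ones.

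**4. The 13-group design.** T9 and T10 have a true ORR of 5% throughout (1,500 trials per row). The assumed active rates for the added groups are HNSCC pretreated 20%, melanoma 40%, RCC pretreated 30%, and RCC naive 240 mg and mCRPC 50% each. In the mixed row T2, T5, T6, T8, T12 and T13 are active.

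| T9 / T10 false positive (%) | n=20 | n=22 | n=24 | n=27/28 | n=30 |
|---|---|---|---|---|---|
| All 13 inactive | 7.7 / 7.4 | 7.5 / 8.0 | 6.3 / 6.3 | 5.1 / 5.0 | 4.7 / 4.3 |
| Mixed | 9.9 / 8.5 | 9.6 / 7.7 | 11.1 / 9.7 | 9.2 / 8.1 | 6.8 / 6.2 |
| All others active | 8.0 / 7.6 | 9.9 / 9.1 | 12.0 / 11.1 | 14.3 / 11.7 | 7.3 / 6.7 |

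The Monte Carlo standard error near 10% is √(0.10 × 0.90 / 1500) ≈ 0.8 points. With every other group exactly at C2, the average of T9 and T10 was 15.0% at n = 20 and 10.2-13.0% at n = 22-26 (1,200 trials). Imposing mu1 < mu2 lowers the rates by about 1 point at most.

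The increase is confined to T9 and T10. In the null runs T12 was at 3.4-3.5% and no group with an interim exceeded 5.0%.

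**5. The mechanism, from the protocol's own table.** In Table 14-17, T10 at 3/22 fails in scenarios 1 and 2 (posterior means 0.1155 and 0.1246, below 0.13) and succeeds in scenario 5 (0.1511), where other groups respond more. With no interim, the false-positive rate at a fixed boundary is the binomial tail at 5%:
- P(X ≥ 3 | 22) = 9.5%
- P(X ≥ 3 | 24) = 11.6%
- P(X ≥ 4 | 30) = 6.1%

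When borrowing lets three responses suffice at n of 22-24, the rate is therefore about 9-12%. At n = 30 the boundary is usually four.

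**6. Plausible n.** Section 4.1.1 fixes only the 20 additional patients per group. The protocol's final-analysis illustrations reach 27 for T9 and 22 or 28 for T10. The Amendment 5 status lists 58 MSS CRC patients in all, and later patients were to start at 240 mg whereas T9 and T10 are 160 mg groups. Since 58 / 2 = 29, at least one of the two groups would have fewer than 30.

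**The case against.** The strongest reply has five parts.

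- **Definition.** The protocol defines the false-positive rate with all groups inactive. On that definition T9 and T10 are at about 4-8%, at most about 1 point above the published 6.8%, and below the published Colon (MSS) 5.8% at n = 27 or more. This stands. It does not rescue the expectation of similarity, because Section 10.8 also presents the mixed-scenario range as evidence of proper control.
- **Scenario choice.** The mixed and active cases put pancreatic (T2) at 25%, yet Section 14.4.5 records 0/14 there, which has probability 0.75^14 ≈ 1.8% at that rate. TNBC, set at 20%, is recorded as 3/30. This stands too: the higher figures are scenario values, not forecasts.
- **The protocol's own 13-group example.** In Table 14-19 scenario 2 four groups succeed. Yet HNSCC pretreated, with the same thresholds as T9 and T10, has a posterior mean of only 0.1245 at 3/27. If four responses were needed, the tail would be P(X ≥ 4 | 27) = 4.4%. Scenario 4 points the other way: TNBC, again with the same thresholds, meets both conditions at 3/30 (mean 0.1342, probability 0.058). The increase depends on which groups are active.
- **The parent cohort had a look.** MSS CRC was split after an interim decision to expand (SAP Sections 1.1.1.1 and 2.8). That is correct, but no published figure reflects that sequence.
- **Consequence.** The study is exploratory and closed for lack of sufficient efficacy (SAP Section 4), so no enrolment decision is at stake.

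A reader might also infer that the 13-group design was never simulated. The documents show only that no such results are reported.

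**Conclusion.** The point holds in a limited form. No 13-group operating characteristics are reported, the SAP describes worked examples as simulations, and the expectation of similarity is unsupported for T9 and T10. Their false-positive rate is about 4-8% with all groups inactive. It is about 8-12%, and up to 14-15% in some runs, when other groups are active and n is about 20-28. It is about 4-7% at n = 30. The comparators are a published maximum of 6.8% (all inactive) and a published mixed range of 4.9-6.9%.

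It would be wrong to conclude that type I error control fails for MSS CRC, or that its false-positive rate simply is 9-12%. The higher figures need both active groups elsewhere and n below 30.

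The estimates assume simultaneous accrual, the active rates stated above, T12 at n = 20, and T9/T10 sizes that the documents do not fix.

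**What to change.** Simulate the 13-group design with Table 10-1 thresholds, no interim for T9, T10 and T12, and the actual T9/T10 sizes or a range such as 20-30. Cover null, mixed and active cases, including cases consistent with data already in the model (for example pancreatic at 0/14 and TNBC at 3/30). Report false-positive rate, power and stopping probability per group, and put these results in place of the Section 10.8 sentence. In SAP Section 3.1, state that hypothetical data examples were evaluated, not that simulations were run.

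The cost is a small amount of simulation and text editing, and a less favourable stated error rate for T9 and T10. Enrolment does not change. The gain is that any MSS CRC result is read against an error rate that belongs to the design used.
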